7.2 Visits and procedures – Participants with post-treatment recurrence of viremia

Re-viremia baseline

 HCV RNA sequencing (Tested at the central laboratory using the research sample collected at baseline)

Re-viremia follow-up – RFU1 (2 weeks post re-viremia baseline), RFU2 (4 weeks post re-viremia baseline) and RFU3 (8 weeks post re-viremia baseline)

- HCV RNA (Finger-stick point of care testing)
- Research sample (EDTA plasma)

7.3 Study Questionnaires

All subjects will undertake a number of study questionnaires at baseline, and selected follow-up visits.

The Behavioural Questionnaire

The study staff will assist participants to complete this questionnaire. The behavioural survey will collect information on the following:

- Demographics
- HIV and drug treatment history
- Drug and alcohol use
- Treatment acceptance and willingness (prior to treatment commencement only)
- Injecting risk behaviours (including information about injecting sharing partners and equipment sharing)

An abbreviated behavioural questionnaire (follow-up) will be administered at subsequent time points during the study.

Health Outcomes Survey (EQ-5D-5L)

The EQ-5D-5L health questionnaire provides a simple descriptive profile and a single index value for health status. This information can then be translated into a health utility, which can be used for cost-effectiveness analyses.

8. Recording and reporting Adverse Events (AEs)

The medications for this study are government approved DAA regimens. Adverse events and adverse drug reactions will be reported to the relevant government agency as per standard practice for government approved medications. Only deaths will be reported as detailed below.

8.1 Reporting deaths

All deaths should be reported within TWO (2) WORKING DAYS of becoming aware of the event to the Kirby Institute by fax or email using the SHARP-C deaths reporting form. Reports should be followed promptly by detailed, written follow-up reports when all information is not included in the initial report. Follow up reports should include all supporting documentation i.e. autopsy reports, as appropriate. Follow-up reports should be reported within TWO (2) WORKING DAYS also. The immediate and follow up reports should identify participants by unique code numbers assigned to study participants rather than personal identification.

Death reports must be submitted to **the Kirby Institute**:

Kirby Institute:

[contact].

[contact]

9. Packaging, labeling, storage and accountability of clinical trial supplies

Study drug is not being provided in this study. Government approved DAA medication will be used and will

be dispensed and stored according to government regulations.

10.Biological samples

10.1 Laboratory supplies and sample processing

Laboratory supplies for collection of research specimens (plasma and whole blood – all sites and PBMCS –

sub-study sites only) will be supplied by the Kirby Institute.

The following blood samples will be collected at time points specified in the schedule of assessments:

1. 10 mL EDTA plasma for HCV RNA testing and future HCV related research (20 mL will be

collected at baseline visit);

2. 4mL whole blood for human genomic DNA analysis collected at the baseline visit only.

Samples will be collected by sites and then processed and stored at -70°C or below at the site local

laboratory for bulk shipment to the Kirby Institute laboratory. Detailed sample processing instructions will

be provided in the laboratory manual.

EDTA plasma samples will be used for study endpoint analysis. HCV viral load will be measured using in-

house and commercial assays. Sequencing of the viral genome will also be performed as a more accurate

means of genotyping. Data generated from the sequencing may also be used to distinguish relapse from

reinfection and to examine the prevalence of mixed infection. Whole blood samples will be used to examine

host factors associated with viral clearance, including but not limited to HLA type, IL28-B, , IP-10, and other

biomarkers.

Sequencing

Sanger sequencing will be performed on all participants with HCV RNA relapse or reinfection in post

treatment follow up to distinguish HCV reinfection from viral relapse (detectable HCV RNA following HCV

virological suppression). Complementary RNA will be generated using SuperScript® VILO™ cDNA Synthesis

Kit (Life Technologies, Carlsbad, CA) with random hexamers. Sequencing of NS5A will be performed on all

participants. A fragment of the HCV genome covering Core, Envelope-1, hypervariable region-1 and beginning of Envelope-2 (E2) will be amplified using a method previously described. Sequencing of NS3/4, NS5A, NS5B, and full-length next generation sequencing may also be performed. Purified amplicons will be sequenced using the Sanger method and sequence chromatograms processed using RECall: a fully automated sequence analysis pipeline. Subtypes will be determined using the Oxford HCV Automated Subtype Tool. Reverse transcription, PCR and sequencing reaction and thermal cycling conditions will be performed as previously described. Further, Sanger sequencing and next generation sequencing will be performed among samples with persistent infection at risk of HCV mixed infection (e.g. treatment non-response).

HCV RNA point of Care testing

Point of care testing for HCV RNA detection will be performed at each visit using the Xpert® HCV Viral Load assay for samples collected by finger-stick capillary whole-blood as described below.

The capillary whole-blood sample is collected from participants via a finger-stick [MiniCollect® Safety Lancet (Order Number 450429), Greiner Bio-One, Monroe, Frickenhausen, Germany] using procedures recommended by the World Health Organization³¹ and collected into a 100µL minivette collection tube [Minivette® POCT 100µl (Order number 17.2111.100), Sarstedt, Nümbrech, Germany]. The Xpert® HCV Viral Load assay is being evaluated as part of this study and is therefore only being used for research purposes, not for diagnostic purposes. As this assay is only being used for research purposes the results and a positive HCV RNA or invalid point of care test should be confirm by a local lab hepatitis C HCV RNA test the Xpert® HCV Viral Load assay will not be given to participants.

10.2 Shipping of biological samples

Samples must only be shipped to the Kirby Institute laboratory on the instruction from the Study Coordinator.

It is the responsibility of each site Principal Investigator to ensure that all site staff handling, packaging, and/or shipping biological samples understand and comply with International Air Transport Association (IATA) regulations relating to the handling and shipping of hazardous goods and/or diagnostic specimens.

10.3 Future use of biological samples

After the samples have been analysed for the study endpoints as specified in the protocol, remaining samples will be stored for use in future Human Research Ethics Committee approved hepatitis C related research. Samples will be stored until all of the samples have been used up or the sample is no longer viable. Additional consent will not be sought for this storage and future use. It is not optional. Subjects

not wishing to have their samples stored or used in future hepatitis C related research will not be eligible to participate in this study.

11. Statistics

The statistical team and investigators at the Kirby Institute will be responsible for analysing the study data.

Primary Objective:

To evaluate the incidence of HCV reinfection following successful DAA therapy among people with chronic HCV infection and recent injecting drug use.

Hypothesis 1.1: The incidence of HCV reinfection following successful DAA therapy will be <8 per 100 person- yrs among people with recent injecting drug use.

Hypothesis 1.2: HCV reinfection will be associated with ongoing daily injecting drug use, and needle and syringe borrowing, and the treatment in the prison. OST and high-coverage access to needle and syringes will be associated with reduced HCV reinfection.

Outcome: Incidence of HCV reinfection following successful DAA therapy.

Statistical analysis: Rates of HCV reinfection will be calculated using person-time of observation. The estimated date of reinfection will be calculated as the midpoint between the dates of the last undetectable HCV RNA test and the first detectable HCV RNA test at the time of HCV reinfection. Time at risk will commence at the date of undetectable HCV RNA at end of treatment and end at the first of estimated date of re-infection, death, loss-to-follow up or end of study. Confidence intervals for rates will be calculated using a Poisson distribution.

Cox proportional hazards analyses (or other appropriate regression models) will be used to estimate crude and adjusted hazard ratios and corresponding 95% CI to evaluate factors associated with reinfection. Factors hypothesised to be associated with reinfection include demographic factors (age, sex), injecting behaviours (recent injecting drug use, daily injecting, type of drug injected, injecting equipment borrowing), use of needle and syringe programs, and opioid substitution treatment with time-updated co-variates.

Sample Size: Overall, based on previous reports of HCV reinfection among recent PWID³⁰, and assuming loss to follow-up is 20% per year, it is estimated that the overall reinfection rate will be 8/100 p-yrs (95%CI 5.7-10.7; 478 p-yrs of follow-up; 38 reinfections). Overall (225 with successful therapy, 38reinfections), we will have 80% power to detect a hazards ratio (HR) of 2.47 or greater (with alpha=0.05) for a variable 50% prevalent (e.g. ongoing injecting drug use).

Secondary Objectives:

4) To evaluate the proportion of participants with undetectable HCV RNA at 12 weeks post end of

treatment (SVR12) following DAA HCV therapy among PWID with chronic HCV infection and recent

injecting drug use;

5) To evaluate the proportion of participants who complete treatment;

6) To evaluate the proportion of participants with undetectable HCV RNA at the end of treatment

Hypothesis 2.1: Reduced response to DAA therapy among recent PWID will be predicted by previous

treatment experiences, cirrhosis, baseline mixed HCV infection and resistance associated substitutions.

Outcome: The primary endpoint for this aim is the proportion of participants with a treatment response

(measured by SVR, undetectable HCV RNA 12 weeks after the completion of therapy).

Statistical analysis: The proportion of people with a response to HCV therapy will be evaluated. Factors

associated with treatment response (as measured SVR) will be assessed by univariate and multivariate

logistic regression analyses. Factors hypothesised to be associated with response to DAA therapy are:

injecting behaviours (recent injecting drug use prior to and during treatment and type of drug injected),

clinical factors (opioid substitution treatment, HCV regimen, fibrosis stage), and virological factors (HCV

genotype, baseline mixed HCV infection, presence of resistance associated variants).

Sample size: Assuming an overall SVR of 90% (225 of 250), the 95% confidence intervals (95%CI) around

this estimate will be 86.0 to 92.8%. This study will have robust power to examine the effect of treatment

setting on SVR: e.g. 80% power to detect an odds ratio of 1.87 or greater (alpha=0.05) for a variable that

is 50% prevalent (i.e. community vs. prison).

Collateral research

Objective: To evaluate injecting behaviours and injecting cessation following successful DAA therapy.

Hypothesis: Daily injecting drug use and needle and syringe borrowing will decrease following the initiation

of HCV therapy.

Outcome: The primary endpoint for this aim is recent (past month) daily injecting drug use. Secondary

endpoints will include the number of days injecting in the past month, recent (past month) injecting drug

use, needle/syringe borrowing, injecting equipment borrowing, attitudes towards reinfection risk, non-

injecting drug use, and opioid substitution therapy.

Statistical analysis: The proportions of individuals reporting behavioural outcomes will be assessed among all individuals longitudinally at all study visits. To account for loss to follow-up and the correlated nature of successive responses among participants, Generalised Estimating Equations (GEE) will be used to evaluate the impact of time in the study on all outcomes. Unadjusted and adjusted GEE models will be specified using a binomial family function, a logit link and an exchangeable correlation structure. Odds ratios with corresponding 95%CIs and p-values will be calculated. Variables hypothesised to be associated with behavioural outcomes will be evaluated using GEE analysis including sociodemographic factors (age, sex, housing), access to harm reduction services (OST and high-coverage NSP), and treatment setting (community vs. prison).

Sample Size: In the overall cohort, this study will have 80% power to detect a significant decrease in daily injecting from 50% to 42% over the study period. GEE models will further improve power and account for the correlated nature of successive visits among participants.

12. Data collection, source documents and record retention

The Principal Investigator and the institution where the study will be conducted will permit study-related monitoring, audits, ethics committee review and regulatory inspection providing direct access to source documents.

Data will be collected on study specific electronic or paper copy case record forms. The Principal Investigator is responsible for ensuring the data collected are complete, accurate and recorded in a timely manner.

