- To evaluate the proportion of participants with undetectable HCV RNA at 12 weeks post end of treatment (SVR12) following DAA HCV therapy among PWID with chronic HCV infection and recent injecting drug use;
- 2) To evaluate the proportion of participants who complete treatment;
- To evaluate the proportion of participants with undetectable HCV RNA at the end of treatment.

Exploratory Objectives

- To evaluate demographic, clinical and virological predictors of HCV reinfection;
- 2) To evaluate demographic, clinical and virological factors associated with SVR12;
- To evaluate injecting risk behaviours during and following HCV treatment;
- To evaluate HCV phylogenetic clustering and molecular epidemiology;
- 5) To evaluate the prevalence of resistance associated substitutions;
- 6) To evaluate the immunovirological changes occurring in the context of treatment, following treatment, and in the setting of post-treatment re-viremia including reinfection and relapse;
- 7) To determine the sensitivity and specificity of the Xpert® HCV Viral Load assay for HCV RNA detection in samples collected by finger-stick capillary whole-blood

Participant population

Participants will be recruited from hospital-based HCV clinics and community-based drug treatment clinics.

Inclusion criteria

1) Participants have voluntarily signed the informed consent form.

- 2) Be ≥18 years of age on day of signing informed consent form.
- 3) Have chronic HCV infection.
- 4) Recent injecting drug use (previous 6 months).
- 5) Eligible for DAA therapy as per the government criteria
- 6) HIV-1 infected participants enrolled in the study must meet the following criteria:
 - a) Have HIV infection documented by any licensed rapid HIV test or HIV enzyme or chemiluminescence immunoassay (E/CIA) test kit at any time prior to study entry (Baseline) and confirmed by a licensed Western blot or a second antibody test by a method other than the initial rapid HIV and/or E/CIA, or by HIV-1 p24 antigen, or plasma HIV-1 RNA viral load.

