The investigators have an excellent track record of conducting high quality cohort studies and clinical trials among PWID in the community¹⁹⁻²³ and prison²⁴, with high participant retention in follow-up. The investigators have developed a network of clinical sites providing HCV care in nine community-based drug treatment clinics^{20, 25}. In SHARP-C the investigators will explore the risk of HCV reinfection and treatment efficacy among recent PWID with chronic HCV and recent injecting drug use.

2. Hypotheses

Primary Hypothesis

The incidence of HCV reinfection following successful DAA therapy will be <8 per 100 person years among people with current injecting drug use.

3. Study objectives

Primary Objective

To evaluate the incidence of HCV reinfection following successful DAA therapy among people with chronic HCV infection and recent injecting drug use.

Secondary Objectives

- 1) To evaluate the proportion of participants with undetectable HCV RNA at 12 weeks post end of treatment (SVR12) following DAA HCV therapy among PWID with chronic HCV infection and recent injecting drug use;
- 2) To evaluate the proportion of participants who complete treatment;
- 3) To evaluate the proportion of participants with undetectable HCV RNA at the end of treatment.

Exploratory Objectives

- 1) To evaluate demographic, clinical and virological predictors of HCV reinfection;
- 2) To evaluate demographic, clinical and virological factors associated with SVR12;
- 3) To evaluate injecting risk behaviours during and following HCV treatment;
- 4) To evaluate HCV phylogenetic clustering and molecular epidemiology;
- 5) To evaluate the prevalence of resistance associated substitutions;
- 6) To evaluate the immunovirological changes occurring in the context of treatment, following treatment, and in the setting of post-treatment re-viremia including reinfection and relapse;
- 7) To determine the sensitivity and specificity of the Xpert® HCV Viral Load assay for HCV RNA detection in samples collected by finger-stick capillary whole-blood;

4. Participant population

Participants will be recruited from hospital-based HCV clinics and community-based drug treatment clinics in Australia, New Zealand and Canada

Inclusion criteria

- 1) Participants have voluntarily signed the informed consent form.
- 2) Be ≥18 years of age on day of signing informed consent form.
- 3) Have chronic HCV infection.
- 4) Recent injecting drug use (previous 6 months).

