Participants who have a positive HCV RNA point of care test during the follow up period will be considered to have post-treatment recurrence of viremia. All patients identified as having post-treatment recurrence of viremia will have an increased follow up schedule for 8 weeks before returning to the standard follow up schedule. Participants once identified as having recurrent viremia will be followed intensely for 8 weeks as per the post-treatment recurrence of viremia schedule of assessments. Once the participant has completed 8 weeks follow up they will continue with 3 monthly follow up visits as per the standard schedule of assessments.

Patients may be offered retreatment with government approved DAA drug regimens. The decision to retreat as well as the regimen and duration will be determined by the treating clinician according to government prescribing guidelines.

[figure not shown]

Figure 2: SHARP-C post-treatment recurrence of viremia schema

6. Treatment of participants

A total of 250 participants will be enrolled with chronic HCV, recent injecting drug use (past 6 months) and initiating DAA HCV therapy. Participants will be seen in hospital-based HCV and community-based drug treatment clinics.

Participants will be treated with a government approved DAA drug regimen which will be prescribed as appropriate for the participants fibrosis stage, HCV genotype and previous treatment experience at the discretion of the treating clinician.

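### Section 11 relies on a prison treatment setting in three places, but the trial recruits only from hospital and community clinics, and the SVR power figure attached to that contrast is wrong even with the label changed

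*Protocol*

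**What the plan says.** **Who is recruited.** Section 4 of the protocol says "Participants will be recruited from hospital-based HCV clinics and community-based drug treatment clinics in Australia, New Zealand and Canada". The synopsis has the same sentence without the countries. Section 5 describes a network of hospital-based and community clinics. Section 6 says "A total of 250 participants will be enrolled with chronic HCV, recent injecting drug use (past 6 months") and adds "Participants will be seen in hospital-based HCV and community-based drug treatment clinics". No prison site, stratum or procedure appears in the population, design, treatment or procedures text.

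**Where section 11 uses prison.**
- Hypothesis 1.2, under the primary objective: "HCV reinfection will be associated with ongoing daily injecting drug use, and needle and syringe borrowing, and the treatment in the prison". The same hypothesis also covers opioid substitution therapy and high-coverage access to needles and syringes.
- The SVR sample-size paragraph: 80% power at alpha 0.05 for an odds ratio of 1.87 or greater, for a variable that "is 50% prevalent (i.e. community vs. prison"). The SVR assumed there is 90%, or 225 of 250.
- The GEE model for injecting behaviour, under Collateral research, whose covariates end with "and treatment setting (community vs. prison").

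The factor lists for the Cox model of reinfection and the logistic model of SVR contain no setting variable of any kind.

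**The concern.** A hypothesis clause, a power claim and a model covariate all need participants treated in prison, and the recruitment text provides none. A covariate with a single observed level drops out of the model, so the clause in Hypothesis 1.2 could never be reported on. The SVR paragraph also assures the reader that the study is well placed to examine treatment setting, when the setting it names does not vary in this cohort.

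The obvious repair is to change the label to hospital versus community clinic. That would keep the odds ratio of 1.87 and the 80% power, so those figures have to be checked against the protocol's own assumptions first.

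**Working it through.** **1. Can the prison contrast be estimated?** The information on a binary covariate is proportional to p(1 − p), where p is its prevalence. Section 11 assumes p = 0.50, giving 0.25. As recruited, p = 0/250 = 0, giving 0. No odds ratio or hazard ratio can be estimated, and the stated power does not apply.

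**2. Does the SVR power figure reproduce for any variable with 50% prevalence?** Inputs from the SVR sample-size paragraph: SVR 90%, N = 250, odds ratio 1.87, alpha 0.05. The paragraph does not state sidedness, so two-sided is taken first.

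Two equal groups of 125 whose SVRs average 90% with an odds ratio of 1.87 have p1 = 0.872 and p2 = 0.928, so d = 0.0550.

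Power = Φ[(d − 1.96 × se0) / se1], where
- se0 = √(0.9 × 0.1 × 2/125) = 0.0379
- se1 = √[(p1(1 − p1) + p2(1 − p2))/125] = 0.0378

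Power = Φ[(0.0550 − 0.0744)/0.0378] = Φ(−0.51) = **30%**. The stated figure is 80%.

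Other readings of the same sentence:

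| Reading | Power |
|---|---|
| 90% average, N = 250, two-sided | 30% |
| Same, one-sided | 42% |
| 90% as the SVR of one group, the other higher | 25% |
| 90% as the SVR of one group, the other lower | 38% |
| 90% average, N = 500, two-sided | 54% |
| 50% outcome, N = 250, two-sided | 69% |
| 50% outcome, N = 250, one-sided | 79% |

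Only the last row comes close to 80%. It needs a 50% response rate, which contradicts the 90% in the same paragraph.

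**3. What can 250 participants detect?** At 50:50 and 90% average SVR, 80% power is reached at 84.7% versus 95.3% (d = 0.1058, se1 = 0.0374): Φ[(0.1058 − 0.0744)/0.0374] = Φ(0.84) = 80%. That is an odds ratio of about **3.65**. For an odds ratio of 1.87, the pooled-variance formula gives n per group = (1.96 × √0.18 + 0.842 × √0.1785)² / 0.0550² ≈ 466, or about **932** in total.

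**4. Sensitivity to the split.** The protocol does not give the hospital/community split. For an odds ratio of 1.87, with the smaller group having the lower SVR, power is about 32% at 25:75 and 23% at 10:90.

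**5. Is the reinfection power statement affected?** Inputs: 38 events, hazard ratio 2.47, 50% prevalence. Schoenfeld power = Φ[√(38 × 0.25) × ln 2.47 − 1.96] = Φ(2.787 − 1.960) = Φ(0.83) = 79.6%. This agrees with the stated 80%. Its example is ongoing injecting, not setting, so it stands.

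**The case against.** **The reach is small, and this stands.** The primary objective is an incidence rate, and predictors of reinfection are an exploratory objective. Hypothesis 1.2 also names daily injecting, borrowing, opioid substitution therapy and needle and syringe access, all of which remain testable. A reader might infer that the whole hypothesis, or the primary objective, cannot be tested. The document does not support that, because only the prison clause fails. Nor do the fitted Cox and SVR models break, since neither factor list contains a prison term.

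**Linked incarceration data might seem to fill the gap, but they do not.** Section 12.2 plans linkage to incarceration records. It is for Australian sites only, participants can opt out, and further ethics approval is needed before any linkage. Being imprisoned at some time is also not the same as being treated in prison, so linkage cannot supply the contrast in section 11.

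**A reader might also infer that clinic type and country are omitted confounders.** The protocol does not show this. All participants must be eligible for government-approved therapy, and the Cox list already includes needle and syringe programs and opioid substitution treatment, with time-updated covariates. That list is worded as open, and final covariate choice is commonly left to a statistical analysis plan, which is not at hand. With 38 expected reinfections and 25 expected SVR failures (250 − 225), extra terms also have a price.

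**The study schema figures are not shown.** They could in principle mention prison, but the synopsis and sections 4 to 6 consistently name only hospital and community clinics.

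**Conclusion.** The point holds as an internal inconsistency. Three statements in section 11 depend on a treatment setting that sections 4 to 6 do not recruit, and the prison effect cannot be estimated. No primary or secondary estimate changes: the reinfection rate and its Poisson interval, the SVR12 proportion and the hazard ratio statement all stand.

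The SVR power claim is wrong apart from its label. On the protocol's own 90% SVR and 250 participants, power for an odds ratio of 1.87 is about 30%, not 80%. This assumes a 50:50 split, a two-sided 5% test and an unadjusted comparison of two proportions. None of the alternative readings that keep the 90% SVR reaches 80%, even with 500 participants. The true hospital/community split is unknown, and power would differ with it.

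**What to change.** 1. Delete the prison clause from Hypothesis 1.2, and the community versus prison contrast from the SVR power statement and the GEE covariates.
2. If treatment setting is kept, define it as hospital-based versus community-based clinic, which is known for every participant, and use that definition throughout section 11.
3. Withdraw the 80% power claim for an odds ratio of 1.87, or restate it. At an assumed 50:50 split, the figure to state is a detectable odds ratio of about 3.65 (84.7% versus 95.3%). If setting is the example, base the figure on the expected hospital/community split.

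Mandatory country terms and a covariate from linked incarceration records are not part of this correction.

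The cost is text changes in three places and one recalculation, with no new data. The downside is a less favourable stated power for factors associated with SVR.
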